Dental Appliance for Parkinson Disease (DAPD)

Official Title: Dental Appliance for Parkinson's Disease

NCT Number: 04082663

Document Date: April 23, 2019

I. SPECIFIC AIMS

The primary objective of this study is to determine if the use of a dental mouthpiece can improve gait and motor signs and symptoms, sleep, or quality of life for people with Parkinson's disease (PD). We will conduct a pilot study with participants who have been diagnosed with PD recruited from the community. For this study, participants will have one in-person study visit where they will be fitted with a dental mouthpiece and complete motor tests while wearing the mouthpiece and while not wearing the mouthpiece. Participants will also complete sleep questionnaires and quality of life questionnaires. Participants will then be asked to take the mouthpiece home and wear it at night while they sleep and during the day, except while eating, for one month. At the end of the month, they will complete the same sleep and quality of life questionnaires administered remotely by mail and answer questions about their experience with the dental mouthpiece.

Specific Aim 1: To determine the immediate effect of a dental mouthpiece on Parkinsonian gait and motor symptoms. A 4.8m GAITRite (CIR Systems, Inc., Franklin, NJ) will be utilized to quantify gait mechanics with and without mouthpiece use. Gait and balance tasks will be assessed.

Hypotheses:

- a. People with PD will show improvements in gait speed with the mouthpiece in place compared to without.
- b. People with PD will show improvements in balance with the mouthpiece in place compared to without.

Specific Aim 2: To determine the longer-term feasibility of use and effect of dental mouthpiece on sleep and quality of life (QOL) for people with PD.

Hypotheses:

- a. People with PD will show improvements in sleep quality and duration after one month of wearing the mouthpiece as compared to baseline.
- b. People with PD will show improvements in health-related quality of life after one month of wearing the mouthpiece as compared to baseline.

II. BACKGROUND AND SIGNIFICANCE

For people with Parkinson's disease (PD) advances in medical treatments have increased lifespans but have not effectively mitigated the decline in function and the characteristic signs and symptoms of the disease. 1, 2 People with PD often report disturbances in sleep, activities of daily living, and general quality of life. Gait and balance dysfunction are known to negatively affect quality of life in this patient population and are considered risk factors for falls. Walking ability appears to be particularly important in this population, as impairments in ambulation tend to precede impairments with other gait-dependent activities. 4

Several clinical reports and case studies have shown assorted benefits from use of a dental mouthpiece in people with PD. Specific characteristics of these mouthpieces differ somewhat across cases, but the mouthpieces are typically modeled after those used for temporomandibular joint disorder. A clinical report for one woman with PD showed improvements in grip strength and subjective improvements in motor function and quality of life while using a mouthpiece. This report relied on observation for determining improvements in motor function and did not report a formal quality of life measure or questionnaire. In another case report, a participant subjectively reported use of a bruxism splint improved their sleep quality and fatigue levels. However, again, no quality of life or sleep measures were reported.

A more recent case study found some objective improvements in selected gait and balance measures in a participant with PD while using a dental mouthpiece. The Four Square Step Test and grip strength in the non-dominant hand showed significant improvements with the mouthpiece compared to the patient's baseline condition without the mouthpiece. Additionally, this participant reported significant increases in quality of life while using the mouthpiece, as evidenced by significant improvements in Parkinson Disease Questionnarie-39 (PDQ39) and Global Rate of Change Scale. The researchers reported the participant's gait mechanics differed with use of the mouthpiece, with the participant holding his arms closer to midline.

The mechanism underlying the mouthpiece's effect on gait and motor function is not well understood. It is possible that because afferent inputs from the trigeminal nerve project to the nucleus raphe of the reticular formation, abnormal input from the mandibular branch of the trigeminal nerve may affect rhythmic motor function and balance. Stimulation of the nucleus raphe can produce rhythmic contractions of muscle groups which could potentially affect gait and posture. A mouthpiece may function to promote a more optimal maxillomandibular vertical interrelationship and reduce irritation or abnormal feedback from the mandibular branch of the trigeminal nerve, or more specifically the auriculotemporal nerve, to the nucleus raphe.

Current knowledge regarding the effects of a mouthpiece on motor function and quality of life in people with PD is limited by slight variance in design between mouthpieces and by the small number of participants studied thus far. Our understanding of the topic is based on a small handful of clinical reports and case studies. By conducting an exploratory pilot study, we will examine whether a mouthpiece can affect motor symptoms and gait in a larger group of participants with PD. Additionally, we will determine whether use of a mouthpiece can improve sleep and quality of life in people with PD. [name], MD, MA, ThM will custom fabricate the mouthpieces for this study. [name] has authored several peer-reviewed, journal-published studies in which he fabricated mouthpieces to treat various symptoms resulting from neurological disorders. 10,11

III. METHODS

Participants

Participants will be recruited from the community.

For inclusion in the study, participants must:

(1) have a diagnosis of idiopathic, typical Parkinson Disease according to the UK Brain Bank Criteria, Hoehn & Yahr stages 1-3;

- (2) stable PD medications for the two weeks prior to baseline visit;
- (3) be able to walk at least 10 meters at baseline with or without an assistive device;
- (4) have their own teeth and/or dentures;
- (5) be willing to try to wear a mouthpiece for one month;
- (6) are over the age of 30; and
- (7) provide written or verbal informed consent.

Exclusion criteria include:

- (1) pre-existing medical conditions that would inhibit full participation in the study's tasks;
- (2) absence of any dentition;
- (3) cognitive impairments indicated by Mini Mental Status Exam (MMSE) score of <24;
- (4) freezing of gait which moderately or severely impacts walking; or
- (5) current use of an oral appliance (e.g., a dental mouthpiece, retainer, or braces).

Measures and Materials

The MMSE will be administered to ensure absence of cognitive impairment. The New Freezing of Gait Questionnaire (nFOG) includes participants watching a short video about freezing of gait and a questionnaire about whether they experience freezing of gait and if so, questions that help describe the types of freezing of gait they experience.

Mouthpiece

Each participant will be fitted with a maxillary orthotic (mouthpiece) fabricated by [name]. The process for fabrication of the mouthpiece will be as follows:

- 1) The participant is seated in a normal straight-backed chair with feet on the floor.
- 2) A dental impression tray is sized appropriately for the participant's lower jaw to ensure that no impingement of soft tissue structures occurs.
- 3) A quick setting dental alginate impression material is mixed for one minute and then placed into the dental impression tray.
- 4) The dental impression tray is filled with the alginate material, and the tray and material are placed into the participant's mouth.
- 5) The tray will remain in the mouth approximately 1 to 2 minutes and will then be removed.
- 6) A fast setting dental stone is placed in the tray.
- 7) The dental stone is allowed to set for one-half hour in the alginate impression.
- 8) The dental stone model is removed from the alginate impression.
- 9) The lower jaw model is trimmed and then taken to the dental vacuum former machine where a poly-vinyl-acetate (medical-dental grade) thermoplastic sheet of material is heated to a temperature to allow deformation of the material.

- 10) The vacuum is turned on and the thermoplastic material is sucked down over the dental stone model. A small 5 mm wide strip of thermoplastic material is placed directly over the occlusal portion of all the mandibular teeth to act as a reinforcement.
- 11) The thermoplastic material is cooled to below room temperature with cold water until stiff.
- 12) All thermoplastic material which approximates any structure but the dental hard tissue (teeth) is removed from a height just above the attached gingival tissue so that the mouthpiece will be entirely tooth borne.
- 13) The occlusal material is adjusted at chairside so that an even continuous contact with the maxillary teeth is created on all teeth from the rear-most molar teeth including anterior teeth. The mouthpiece will then have the general appearance of a "horse shoe" in shape.
- 14) All areas which contact oral soft tissue on the perimeter of the device will be smoothed to allow placement without any trauma or discomfort to any tissue in the participant's mouth.
- 15) The mouthpiece will be placed in the participant's mouth for a period of about ten minutes to ensure there is no interference with any normal jaw and biting movements.

The mouthpiece is fabricated with polyvinyl ethylene acetate which is non-toxic to humans. There are similar mouthpieces sold over the counter by pharmacies for patient use without a physician/dentist's prescription.

Participants will be instructed to return the mouthpiece at the end of the study period.

Motor assessments

Movement Disorder Society-Unified Parkinson's Disease Rating Scale Part III (MDS-UPDRS-III) Motor subsection will be used to assess disease severity.

The GAITRite system will be used to assess gait performance. The GAITRite is a portable electronic walkway mat (600 cm long and 64 cm wide). All participants will walk along the mat so that imbedded sensors are activated by foot pressure and deactivated when pressure is released. A computer will process the footsteps for gait velocity (cm/s). The mat is located in a well-lit room, with starting and ending limits marked one meter from the mat to prevent recording acceleration and deceleration phases.

Balance will be assessed using the Mini-BESTest. The Mini-BESTest is a 14-item evaluation designed to assess a variety of balance components.

Quality-of-life questionnaires

Parkinson's Disease Questionnaire-39 (PDQ-39) contains 39 self-report items designed specifically for people with PD. There are eight subscores that are calculated along with a total score.

Parkinson's Disease Sleep Scale (PDSS) contains 15 self-report items designed specifically to assess various indicators of sleep quality in people with PD.

Participant information

Participants will fill out a demographic form, a medication form, and medical comorbidity form at the in-person visit, and note any changes in their health or medications after wearing the mouthpiece for one month.

Journal

Participants will keep a journal documenting how long they wore the mouthpiece at night and during the day, reasons for taking it out, and can make comments about the mouthpiece.

Exit questionnaires

Participants will complete an open-ended exit questionnaire regarding their experience with the mouthpiece and the Global Rate of Change Scale (GRC) after wearing the mouthpiece for one month.

Protocol

A phone screen will be used to screen for preliminary study suitability. If the potential participant passes the phone screen and would like to enroll in the study, we will then schedule them for their in-person visit.

The first visit will be in-person on the ground floor of the Movement Science Research Center at [name]. The study visit will follow the following schedule:

Informed consent, MMSE, nFOG (15 minutes): A trained researcher will review the informed consent document with the participant, outlining the study objectives and ensuring the participants have the opportunity to ask the researcher any questions they may have regarding the study and procedures. If the participant wants to continue, they will sign the consent form. The MMSE will be performed to screen for cognitive impairments which would affect study participation. The nFOG will provide us with information about freezing of gait if applicable.

Motor Assessment #1 without mouthpiece (45 minutes): MDS-UPDRS-III, GAITRite, Mini-Bestest (order will be randomized)

Dental Measurements (15 minutes): [name] will take dental measurements for the purpose of creating a custom-fitted mouthpiece as outlined in the Methods section.

Questionnaires, Medical History, Medications (30 minutes): The participants will complete demographic, medical history/medications forms, sleep and quality of life questionnaires while their mouthpiece is being fabricated.

Mouthpiece in (25 minutes): After their mouthpiece has been fabricated and adjusted (smoothed as needed), participants will sit with the mouthpiece in for 25 minutes.

Motor Assessment #2 with mouthpiece (45 minutes): MDS-UPDRS-III, GAITRite, Mini-Bestest, (order will be randomized)

Participants who take medication for Parkinson symptoms, will be asked to take their medication 30 minutes before arrival to ensure participants are in the "on" phase for the motor tasks.

At completion of the in-person visit, participants will be instructed to use the mouthpiece as much as possible for the next month. Participants will be informed they can take the mouthpiece out while eating and will be instructed to keep track of how long they wear the mouthpiece each day by journal entry.

Follow-up will occur one month later.

Questionnaires, Medical History, Medications (30 minutes): The participants will complete sleep and quality of life questionnaires, record any changes in their medical history or medications, and complete an open-ended questionnaire regarding their thoughts on the mouthpiece and the GRC.

Randomization Method

The order in which the motor assessments are given in regards to wearing the mouthpiece or not will be randomized for each participant. The motor tasks (disease severity, gait, balance) will be randomized within each participant.

Safety and Adverse Events

The research team will do everything possible to ensure safety of all participants over the course of this study. The adverse event most likely to occur in this study is risk of falling while walking. Participants will be fitted with a gait belt. Members of the research team are trained in fall prevention and will closely monitor all participants throughout all aspects of the study in case of a need to assist with balance to prevent a fall. In the case of an adverse event, emergency medical care will be sought immediately if needed. Any serious adverse events will be reported to the local IRB immediately. Occurrence of an adverse event will be noted in a participant's file.

Potential risks will be addressed in the following ways:

- a) Discomfort in answering questionnaires: Participants may refuse to answer any questions they prefer not to answer.
- b) Loss of confidentiality: Loss of confidentiality is highly unlikely. To safeguard against this, we will comply with all HIPAA regulations. Data will not be identified by participant name. All data will be coded, and code sheets will be stored in locked files.
- c) Stumbling during locomotion: Participants will be closely attended by a trained research staff member during walking and fitted with a gait belt. Walking will be performed in a large, open space and the staff member will be prepared to assist participants who may stumble.
- d) Falling: Participants will be closely attended by a trained assistant who will ensure the safest of conditions. It is unlikely that participants will experience falls during testing or will be injured as the result of a fall. If a participant appears unsteady, breaks will be encouraged or testing will be terminated.
- e) Fatigue from walking: Rest breaks will be provided as needed.

Dental Appliance for Parkinson Disease (DAPD)

f) Discomfort or irritation while being fitted for the mouthpiece or while wearing the mouthpiece: the participants may remove the mouthpiece at any time.

Benefits

We do not yet know the full extent to which the mouthpiece may improve symptoms associated with Parkinson disease. This study may help inform future treatment techniques to improve motor and non-motor function in people with PD.

Interim Monitoring and Early Stopping

Data will be monitored throughout the study and, should any issues arise, we will adjust our protocol and submit any changes to the IRB project for review. We will not conduct interim data analyses.

Statistical Analyses Plan

We will use paired t-tests to determine if there are differences between conditions (with mouthpiece vs without mouthpiece). We will also use paired t-tests to compare sleep and quality of life questionnaires from baseline (prior to study) to follow up (after one month of mouthpiece use).

R will be used for data analysis across all aims.

Power

Because of the exploratory nature of this pilot study and relative lack of information in the literature, no formal power analysis was conducted.

References:

- 2. Shulman LM. Understanding disability in Parkinson's disease. Mov Disord 2010;25 Suppl 1:S131-5.
- 4. Ellis TD C, JT, Earhart GM, Ford MP, Foreman KB, Thackeray A, Thiese MS, Dibble LE. Identifying clinical measures that most accurately reflect the progression of disability in Parkinson disease. Parkinsonism Relat Disord 2016;25:65-71.

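### Does a primary objective joined by the word or, with no named primary outcome, need a single primary test in this pilot?

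*Combined protocol and SAP*

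**What the plan says.** Section I (Specific Aims) gives one primary objective: to "determine if the use of a dental mouthpiece can improve gait and motor signs and symptoms, sleep, or quality of life". It divides this into two aims with two directional hypotheses each: gait speed (1a) and balance (1b), with against without the mouthpiece at one visit; and sleep (2a) and health-related quality of life (2b), one month against baseline. None is ranked above another.

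The Statistical Analyses Plan is short. For Aim 1: "We will use paired t-tests to determine if there are differences between conditions (with mouthpiece vs without mouthpiece". For Aim 2: "We will also use paired t-tests to compare sleep and quality of life questionnaires", baseline against follow-up. No significance level, sidedness, test order, adjustment or success rule is given. Under Power: "Because of the exploratory nature of this pilot study and relative lack of information in the literature, no formal power analysis was conducted". No interim analyses are planned.

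Two other places bear on the reading. Section II calls the study an exploratory pilot, speaks first of motor symptoms and gait, and then says: "Additionally, we will determine whether use of a mouthpiece can improve sleep and quality of life in people with PD". Under Motor assessments in section III, the MDS-UPDRS Part III has a descriptive role ("Motor subsection will be used to assess disease severity") and gait is reduced to one sensor-recorded quantity ("A computer will process the footsteps for gait velocity (cm/s").

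**The concern.** The objective is phrased as a question to be settled, and its list of domains is joined by the word or. Read literally, an improvement in any one domain answers it. With several unadjusted tests and no outcome named in advance, the authors could choose the most favourable result afterwards and report that the mouthpiece improves Parkinson's disease. The error rate of that composite claim exceeds the error rate of any single test.

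The Power section uses the exploratory label only to explain the missing power analysis. It does not say that the p-values are descriptive. At stake is a false statement of benefit for a device with little prior evidence.

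**Working it through.** **Plan's own figure.** There is none to reproduce: the documents give no significance level, sample size, power or correlation.

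**Inputs**
- Number of tests: four, one per hypothesis (section I).
- Level: two-sided 0.05 per test, so 0.025 in the direction of improvement (assumed; the plan's wording about differences fits a two-sided test).
- No true effect and no bias (assumed).
- Common correlation ρ between outcomes: not given, so varied.

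**One hypothesis reported on its own.** The false-improvement rate is 0.025, whatever the other three show.

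**Any one of four, independent.** 1 − 0.975^4 = 1 − 0.9037 = 0.0963. The Bonferroni bound is 4 × 0.025 = 0.10.

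**Any one of four, equally correlated** (large-sample): P = 1 − ∫ φ(z) · Φ[(1.96 − √ρ·z)/√(1−ρ)]^4 dz.

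| ρ | Chance of at least one false improvement | Excess over 2.5% (points) |
|---|---|---|
| 0 | 9.6% | 7.1 |
| 0.3 | 8.7% | 6.2 |
| 0.5 | 7.8% | 5.3 |
| 0.7 | 6.5% | 4.0 |
| 0.9 | 4.7% | 2.2 |

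With correlation 0.5 within each aim and 0 between aims, one pair gives 0.0454, so the four give 1 − (1 − 0.0454)^2 = 0.0887.

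**Small-sample check.** Simulated paired t-tests (100,000 runs, assumed n = 20) give 9.6% at ρ = 0 and 6.6% at ρ = 0.7. At n = 10 the figures are 9.8% and 6.8%.

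**Sensitivity to the count.** Four is a low count. Testing MDS-UPDRS Part III as well gives 1 − 0.975^5 = 0.1189 if independent. Adding the eight PDQ-39 subscores makes 4 + 1 + 8 = 13 tests and 1 − 0.975^13 = 0.280 if independent, or 12.0% at ρ = 0.7. Hypothesis 2a also joins sleep quality with duration and could be split.

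**What one primary outcome would gain.** It returns the headline claim to 2.5%, but only without bias. Participants know when they wear the device. Suppose awareness or test order shifts the mean paired difference by d standard deviations. A noncentral t with n − 1 degrees of freedom and noncentrality d√n then gives, for one outcome and assumed n = 20 (n = 15 to 30 in brackets):
- d = 0.1: 6.2% (5.5% to 7.6%)
- d = 0.2: 13.4% (10.8% to 18.4%)

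At d = 0.2 a single named outcome therefore exceeds the whole no-bias range for four tests.

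**What the wording supports.** The larger figures describe a pooled claim that any one win is success. Section I does not stop at the broad objective; it separates it into four hypotheses, each tied to its own measure. An analyst following the plan runs a paired t-test for each and reports each by name. Nothing in the analysis section combines them.

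**The case for a change.** The strongest case for a change is that silence does not protect. The word or stands in the primary objective itself, so one nominally significant result satisfies it as written. Section II returns to the language of settling a question for sleep and quality of life immediately after calling the study exploratory, and the order in which that section mentions the domains is narrative, not a hierarchy. Naming an outcome would take a few sentences and no extra data. Gait velocity is an obvious candidate: it is the first hypothesis and is recorded by sensors.

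Much of this stands. The plan does leave the headline open, the arithmetic is right, and a sentence on how the p-values are to be read would do no harm.

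It does not establish that the plan produces a wrong result. The exploratory description is not confined to the Power section: section I calls the study a pilot, and section II applies exploratory pilot to the whole of it. The remedy also has a price. Making gait primary would move both effect hypotheses of Aim 2 out of the primary objective, although they are the only outcomes measured after a month of use. Formal adjustment would keep all four in play (two-sided 0.0125 each, 1 − 0.99375^4 = 0.0248 if independent), at the cost of power in a study with no stated sample size. Statisticians could reasonably differ on either choice.

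**Conclusion.** No change is needed. The omission is real, but it is missing detail that an analyst fills sensibly: four paired comparisons, each reported under its own hypothesis with its mean difference and confidence interval, and read as pilot evidence. On that reading each hypothesis has a 2.5% false-improvement rate.

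The rate becomes 9.6% (independent), 6.5% (ρ = 0.7) or 4.7% (ρ = 0.9) only if someone pools the four into a claim that the plan neither makes nor excludes. Those figures assume exactly four tests at two-sided 0.05, no true effect and no bias. They are not bounds: higher correlation lowers them, and testing further scores raises them. Choosing a single primary outcome is a fair trade-off for the sponsor to weigh, not a correction.

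One neighbouring matter is separate. The visit schedule under Protocol fixes the first session ("Motor Assessment #1 without mouthpiece (45 minutes): MDS-UPDRS-III, GAITRite, Mini-Bestest (order will be randomized"), while Randomization Method says the order of wearing or not wearing the device is randomized. Those two sections must be reconciled in their own right; naming a primary outcome would not do it.

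### Hypothesis 2a predicts longer sleep at one month, but the plan identifies no measure of sleep duration at either time point and no duration variable to test

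*Combined protocol and SAP*

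**What the plan says.** Hypothesis 2a (I. Specific Aims, Specific Aim 2) reads: "People with PD will show improvements in sleep quality and duration after one month of wearing the mouthpiece as compared to baseline". Quality and duration are listed as separate outcomes, each compared with baseline.

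The Methods section, under Quality-of-life questionnaires, names two instruments. The PDQ-39 covers quality of life. The PDSS is the only sleep instrument, and the protocol says that it "contains 15 self-report items designed specifically to assess various indicators of sleep quality in people with PD".

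The visit schedule (Methods, Protocol) has participants complete the "sleep and quality of life questionnaires while their mouthpiece is being fabricated". At one month, the study overview in Specific Aims says "they will complete the same sleep and quality of life questionnaires administered remotely by mail". The follow-up entry in the schedule agrees: "The participants will complete sleep and quality of life questionnaires, record any changes in their medical history or medications".

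The Journal section says: "Participants will keep a journal documenting how long they wore the mouthpiece at night and during the day". At the end of the in-person visit participants are "instructed to keep track of how long they wear the mouthpiece each day by journal entry".

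For sleep and quality of life, the Statistical Analyses Plan uses paired t-tests to "compare sleep and quality of life questionnaires from baseline (prior to study) to follow up (after one month of mouthpiece use". It names no score, item or duration variable.

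**The concern.** A before-after comparison of sleep duration needs the same duration variable recorded in the same people at both times. The plan identifies no such variable at either time, so part of a stated, directional hypothesis has no specified test.

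Two problems could follow at reporting. A change in PDSS score might be presented as support for the whole of hypothesis 2a, including duration. Or a duration variable might be chosen after the data have been seen.

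Timing makes this more than missing detail. If hours slept are not asked before the month of wear, no later analysis can supply them. The only substitute would be a participant's recollection of sleep a month or more earlier, given after they have formed a view of the device.

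**Working it through.** The plan gives no figure to reproduce here: it states no sample size, alpha, effect size or standard deviation. The check is a trace of hypothesis 2a through every place where a duration variable could appear.

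| Source | What it is described as recording | Baseline | One month | Hours slept identified? |
|---|---|---|---|---|
| PDSS | Indicators of sleep quality | Yes | Yes | No |
| PDQ-39 | Quality of life: eight subscores and a total | Yes | Yes | No |
| Journal | Mouthpiece wear time, reasons for removal, comments | No | During the month | No |
| Exit questionnaire | Open-ended experience with the device | No | Yes | No |
| Global Rate of Change Scale | Given after one month of wear | No | Yes | No |
| Medical history and medication forms | Health and medications, then changes in them | Yes | Yes (changes) | No |
| Statistical Analyses Plan | Paired t-tests on questionnaires | – | – | No |

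The journal comes closest, but it fails on two counts. Wear time at night is not sleep time, and there is no record from before the device was fitted.

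**Size of the gap.** The four hypotheses predict five improvements:
- gait speed (GAITRite velocity)
- balance (Mini-BESTest)
- sleep quality (PDSS)
- sleep duration (no measure identified)
- health-related quality of life (PDQ-39)

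Four of the five have a named instrument at both assessments.

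**Cost of adding a duration item.** These figures describe the remedy; the finding does not depend on them. The documents name five outcomes that could receive a paired test: MDS-UPDRS-III, gait velocity, Mini-BESTest, PDSS and PDQ-39 total. Testing the eight PDQ-39 subscores as well gives 5 + 8 = 13. Assuming two-sided alpha of 0.05 and independent tests (neither is in the documents), the chance of at least one false positive is 1 − 0.95^k:
- k = 5: 1 − 0.95^5 = 22.6%; k = 6: 1 − 0.95^6 = 26.5%
- k = 13: 1 − 0.95^13 = 48.7%; k = 14: 1 − 0.95^14 = 51.2%

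**Precision of the added item.** The half-width of the 95% confidence interval for mean paired change is t(0.975, n−1) × SD / √n. No sample size is given, so I assume n = 10 to 30 and an SD of paired change of 1.0 to 1.5 hours:
- n = 10: 43 to 64 minutes
- n = 20: 28 to 42 minutes
- n = 30: 22 to 34 minutes

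**The case against.** The strongest reply is that the documents cannot show that duration goes unmeasured. The items of the PDSS, the PDQ-39 and the forms are not reproduced, and indicators of sleep quality could include one on hours slept. This stands as a limit on the claim: what can be shown is that no duration outcome is identified. It does not remove the gap, because an item buried in a total score is not a duration outcome unless the plan names it and analyses it on its own. The plural in sleep questionnaires is weak evidence of a second instrument. The text uses the same plural for quality of life, where only the PDQ-39 is named.

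Second, the Statistical Analyses Plan names no individual variable for any outcome, so its silence on duration is not special. That is fair, and the weight of the finding rests on Methods. The other outcomes can be traced from hypothesis to a named instrument; duration cannot.

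Third, this is an exploratory pilot, and duration appears as an outcome only in hypothesis 2a. That bounds the importance and explains the absence of a power calculation. It does not explain a stated prediction with no specified measure.

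Fourth, a single self-report item may be too imprecise to be useful and adds a test. The half-widths above bear this out: modest changes could be missed. The false-positive rates are also only indicative. Independence is implausible, particularly when the PDQ-39 total is counted alongside its own subscores. These points are reasons to consider naming an existing item or amending the hypothesis; they do not justify leaving the mismatch in place.

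**Conclusion.** The concern holds. As written, the duration part of hypothesis 2a has no identified measure at baseline or one month and no specified test. One of five predicted improvements is affected. The sleep-quality part of hypothesis 2a, hypothesis 2b, Aim 1 and the primary objective are not.

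The conclusion rests on reading the documents and on no numerical assumption. It would change in one respect only: if an existing questionnaire item records hours slept, the defect is that this item has not been named as the outcome, rather than that nothing is collected. The point should be corrected, and preferably before the first baseline visit, because a missing baseline value cannot be recovered afterwards except by recall.

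**What to change.** Choose one of three routes.

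1. **Add an item.** Put one self-report question on usual hours of actual sleep per night, worded identically, in the baseline pack and the one-month mailed pack. The baseline pack is completed during fabrication, so before any wear. In the Statistical Analyses Plan, name it as the duration outcome, report mean paired change with a 95% confidence interval separately from the PDSS, and label it exploratory. The cost is one question in each of two existing packs. The answer will be imprecise, the comparison remains uncontrolled, and there is one more test, with the consequences worked out above.
2. **Name an existing item.** If a questionnaire already in use records hours slept, identify that item as the duration outcome and analyse it in the same way. This needs no new data collection, though it still adds a separately analysed outcome.
3. **Amend the hypothesis.** Delete *and duration* from hypothesis 2a and limit the sleep conclusion to PDSS sleep quality. This costs two words and adds no test, but the study then says nothing about duration.

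The first or second route suits a team that wants to learn about duration; otherwise the third restores consistency. None of them alters visits, eligibility or clinical management.
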